7.1.1 Study specific discontinuation of study medication criteria

Patients should be withdrawn from study medication for the following reasons:

- If they experience a clinically significant progression of disease such as:
 - Kidney or liver or multi-organ failure
 - Need for mechanical ventilation
 - Stage 5, end stage kidney disease (GFR <15 mL/min)
 - ALT and/or AST increases to > 5 times upper limits of normal
- Pregnancy in a female patient
- If a patient who does not meet eligibility criteria is inadvertently randomized and received study medication

Other criteria that may or may not require permanent discontinuation of study medication include but are not limited to:

Adverse event, lack of efficacy, protocol deviation, non-compliance, study closed/terminated, investigator discretion, or patient withdrawal of consent.

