- Any abnormal laboratory test results (e.g., hematology, clinical chemistry) or other safety assessments (e.g., ECG, radiological scans, vital signs measurements), including those that worsen from baseline, considered clinically significant in the medical and scientific judgment of the Investigator.
- Exacerbation of a chronic or intermittent pre-existing condition including either an increase in frequency and/or intensity of the condition.
- New conditions detected or diagnosed after study medication administration even though it may have been present before the start of the study or those associated with underlying disease including expected progression, signs, or symptoms of the disease/disorder being studied.
- Signs, symptoms, or the clinical sequelae of a suspected drug-drug interaction.
- Signs, symptoms, or the clinical sequelae of a suspected overdose of either study medication or a concomitant medication. Overdose per se will not be reported as an AE/SAE unless it is an intentional overdose taken with possible suicidal/self-harming intent. Such overdoses should be reported regardless of sequelae.
- “Lack of efficacy” or “failure of expected pharmacological action” per se will not be reported as an AE or SAE. Such instances will be captured in the efficacy assessments. However, the signs, symptoms and/or clinical sequelae resulting from lack of efficacy will be reported as an AE or SAE if they fulfil the definition of an AE or SAE.

Events NOT Meeting the AE Definition

- The disease/disorder being studied.
- Medical or surgical procedure (e.g., endoscopy, appendectomy): the condition that leads to the procedure is the AE.
- Situations in which an untoward medical occurrence did not occur (social and/or convenience admission to a hospital).

- Anticipated day-to-day fluctuations of pre-existing disease(s) or condition(s) present or detected at the start of the study that do not worsen.

Definition of SAE

If an event is not an AE per definition above, then it cannot be an SAE even if serious conditions are met.

An SAE is defined as any untoward medical occurrence that, at any dose:

a) Results in death

b) Is life-threatening

The term ‘life-threatening’ in the definition of “serious” refers to an event in which the patient was at risk of death at the time of the event. It does not refer to an event, which hypothetically might have caused death, if it were more severe.

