	Adverse Events (AEs) between Day 1 – 29 or discharge and Day 60.	event. Time to combined AE (death, SAE, Severe AE or ET/W from study medication) = elapsed time (in days) from Day 1 to the earliest date of any of the events through hospitalization, Day 29 and Day 60.
	Vital signs during hospitalization between Day 1 – Day 29 or discharge.	 Respiration rate (breaths per minute) Heart rate (beats per minute) Oxygen saturation (SpO2) Supplemental oxygen use (yes/no) Body temperature (Celcius) Blood pressure (mmHg) Level of consciousness graded on the AVPU scale (Alert, Verbal = voice response present, Pain = pain response present, Unresponsive). Other parameters may include (but are not required per protocol): Dehydration status, Fraction of inhaled oxygen (FiO2), Sternal capillary refill time
	Laboratory values during hospitalization between Day 1 – Day 29 or discharge.	

pg. 17 Confidential

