8.7 Safety Analysis

Time to first combined event.

Any patients that are lost to follow-up or terminated early prior to experiencing any of the events will be censored at the day of their last observed assessment.

Patients who complete follow-up but do not experience any of the events will be censored at the day of their Day 29 visit.

pg. 20 Confidential

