9.5 Safety Analysis

Safety endpoints include SAEs and AEs (Protocol Appendix 4). Adverse events will be analyzed using quantitative and qualitative measures.

Treatment-emergent adverse events will be summarized by treatment group for all AEs, related AEs, serious adverse events, deaths, adverse events leading to discontinuation of study medication or to withdrawal from study, adverse events of different severity and adverse events of different chronicity.

Treatment-emergent adverse events will be coded using MedDRA and summarized by system organ class and preferred term for each treatment group.

The time to the composite AE endpoint (death, SAE, severe AE or ET/W of treatment during first 29 days) will be compared between treatment groups using the log-rank test and difference between treatment arms will be expressed as a difference in proportions as measured by the Cochran Mantel-Haenzel (stratum)-weighted estimator based on the fitted logistic regression model

• If '0' events, proportions will be presented.

Summaries of the results of the safety analysis are displayed in Table 12.

Table 12. Clinical study RPL554-COV-201 analysis tables - Safety Analyses.

Table #	Table Name
14.3.1	Time to first composite AE (Safety Analysis Set)
14.3.2	Number/Proportion Treatment emergent adverse events summary (Safety Analysis Set)
14.3.3	Number/Proportion TEAEs by system organ class and preferred term (Safety Analysis Set)
14.3.4	Number/Proportion TEAEs leading to discontinuation of study treatment by system organ class and preferred term (Safety Analysis Set)
14.3.5	Number/Proportion TEAEs causally related to the study treatment by system organ class and preferred term (Safety Analysis Set)
14.3.6	Number/Proportion TEAEs by maximum severity by system organ class and preferred term (Safety Analysis Set)
14.3.7	Number/Proportion Serious TEAEs by system organ class and preferred term (Safety Analysis Set)
14.3.8	Number/Proportion Serious TEAEs causally related to the study treatment by system organ class and preferred term (Safety Analysis Set)
14.3.9	Number/Proportion Serious TEAEs by maximum severity by system organ class and preferred term (Safety Analysis Set)
14.3.10	Number/Proportion Serious TEAEs leading to discontinuation of study treatment by system organ class and preferred term (Safety Analysis Set)
14.3.11	Number/Proportion TEAEs with an outcome of death by system organ class and preferred term (Safety Analysis Set)

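### The composite safety endpoint counts any early stop of study medication as an adverse event whatever the reason, and the SAP leaves study exit during dosing unassigned between event and censoring

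*SAP*

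**What the plan says.** Table 5 in SAP section 7.2 lists, under safety, "Time to combined AE (death, SAE, Severe AE or ET/W from study medication", timed from Day 1. SAP section 9.5 gives the same four components: "The time to the composite AE endpoint (death, SAE, severe AE or ET/W of treatment during first 29 days". It plans a log-rank test and a difference in proportions between arms. Neither place restricts the fourth component by reason. ET/W is absent from the SAP abbreviation list. The nearest expansion is the Early Termination / Withdrawal column of the protocol's Schedule of Activities.

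Protocol section 7.1 names the patient's own request among the grounds for stopping study medication and requires the reason to be documented. Section 7.1.1 calls for withdrawal from medication of an ineligible patient who was randomized and dosed in error. It then lists further grounds that may or may not lead to a permanent stop: "Adverse event, lack of efficacy, protocol deviation, non-compliance, study closed/terminated, investigator discretion, or patient withdrawal of consent".

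On censoring, SAP section 8.7 says: "Any patients that are lost to follow-up or terminated early prior to experiencing any of the events will be censored". It does not say whether the termination meant is of medication or of the study.

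**The concern.** The endpoint is called a combined or composite AE, but one of its four components need not involve an adverse event. A patient who stops by preference, or because the site dosed someone ineligible, would enter the numerator alongside deaths and SAEs. The SAP commits to no other between-arm test on safety; the log-rank tests for selected AEs in protocol section 10.5 are optional. With 30 and 15 patients, a few such stops could change how the composite reads.

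The censoring rule adds a second uncertainty. An inpatient who leaves the study during dosing also stops medication at that moment. Table 5 suggests an event and section 8.7 suggests censoring, and no rule settles it. Two programmers could code the same patient differently.

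**Working it through.** The plan gives no event rate, power or expected number of withdrawals for the composite, so it has no figure to reproduce. The check compares the texts and then sizes the effect under assumed counts.

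**Who is an event, who is censored**

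- *Stops medication for a non-AE reason and stays in follow-up.* Protocol 7.1 allows this, and the SAP disposition shell (Table 14.1.1) has a row for it. Under Table 5 and section 9.5 as worded, this is an event. The footnote to shell 14.3.1 says the time row considers those who experienced adverse events, and this patient had none. The two do not agree.
- *Has already stopped medication early, then leaves the study.* The event has occurred. Section 8.7 censors only patients with no earlier component event, so there is no censoring and no conflict.
- *Leaves the study after dosing has ended at discharge, with no component event.* Censored under section 8.7. No conflict.
- *Leaves the study while still on medication, with no other component event.* Medication stop and study exit fall on the same day. This case is unassigned.

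**Size**

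Inputs: 30 ensifentrine and 15 placebo patients (SAP 6.1). One patient with no other component event who is counted because of a non-AE stop adds 1/30 = 3.3 points or 1/15 = 6.7 points. Three in one arm add 3/30 = 10.0 or 3/15 = 20.0 points. If the patient has another component event later, the proportion does not change, but the event time moves earlier.

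The table uses raw proportions (ensifentrine minus placebo). All counts are assumed, and Fisher's exact test stands in for the log-rank test.

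| Other events (E, P) | Non-AE stops (E, P) | Difference if counted | Difference if not counted | Fisher p, counted / not |
|---|---|---|---|---|
| 6/30, 3/15 | 3, 0 | 9/30 − 3/15 = +10.0 | 0.0 | 0.722 / 1.000 |
| 6/30, 3/15 | 0, 3 | 6/30 − 6/15 = −20.0 | 0.0 | 0.174 / 1.000 |
| 3/30, 3/15 | 0, 3 | 3/30 − 6/15 = −30.0 | −10.0 | 0.042 / 0.384 |
| 6/30, 3/15 | 4, 2 | 10/30 − 5/15 = 0.0 | 0.0 | 1.000 / 1.000 |
| 3/30, 3/15 | 4, 2 | 7/30 − 5/15 = −10.0 | −10.0 | 0.496 / 0.384 |

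A split in the 2:1 allocation ratio raises both proportions and leaves the difference where it was. An imbalance moves the difference in either direction. The third row crosses 5% with no safety event added, but it takes three such stops, all in the smaller arm.

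**The case against.** **All-cause stopping is a legitimate tolerability measure.** The objective covers safety and tolerability, and counting every stop avoids judging reasons. This stands as a case for reporting all-cause discontinuation. It does not justify merging it into an endpoint labelled as an AE.

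**The component may have been meant as AE-linked.** The endpoint's name and the shell 14.3.1 footnote point that way. That is possible, but Table 5 and section 9.5 do not say so. If it was the intent, the fix only writes it down.

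**Nothing would be hidden.** Withdrawals are shown by reason in Table 14.1.1, and deaths, serious TEAEs and TEAEs leading to discontinuation have their own tables. This limits the harm. The tested comparison would still rest on the mixed composite.

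**The size is illustrative.** Any single patient weighs 1/30 or 1/15 on any endpoint here, the counts are assumed, and the trial is blinded, unpowered and exploratory. All of this stands.

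A reader might infer two stronger points that the documents do not support:

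- *That the same patient is both an event and censored.* Section 8.7 applies only before any component event, so a patient who already has an ET/W event is not censored. Elsewhere the SAP separates leaving the study (section 8.5) from stopping dosing (the listings in section 10).
- *That lack-of-efficacy stops on placebo would mask harm on ensifentrine.* Protocol Appendix 4 does say that lack of efficacy "per se will not be reported as an AE or SAE. Such instances will be captured in the efficacy assessments". It goes on to make the resulting signs and sequelae reportable where they meet the AE definition, and it counts expected disease progression as an AE. Many such patients could already be events through the SAE or severe-AE components, so the masking argument is speculation.

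**Conclusion.** The point holds in limited form. As written, Table 5 and section 9.5 score non-safety stops of study medication as composite AE events, although the protocol expects stops of that kind. Separately, ET/W is undefined, and study exit during dosing is assigned to neither event nor censoring.

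The size is 3.3 points per affected ensifentrine patient and 6.7 per affected placebo patient, for patients with no other component event. How many there will be, and in which arm, is an assumption; the direction is unknown, and a 2:1 split leaves the difference unchanged. Because all analyses are exploratory, the consequence is for how the composite is interpreted and carried into later studies, not for a confirmatory error rate. It is worth correcting because the correction is cheap.

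**What to change.** - **SAP Table 5 and section 9.5:** replace the ET/W component with discontinuation of study medication due to an AE, the category already tabulated in Table 14.3.4.
- **SAP section 8.7:** state that patients who stop medication for any other reason stay at risk while followed and are censored when study follow-up ends. Say explicitly that this covers study exit and medication stop on the same day without an AE.
- **Reporting:** show all-cause discontinuation separately, by reason, and do not label it an AE. This keeps the tolerability information.

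The same edit should reconcile other conflicts on this endpoint. Table 5 runs to "the earliest date of any of the events through hospitalization, Day 29 and Day 60", whereas section 8.7 says "Patients who complete follow-up but do not experience any of the events will be censored at the day of their Day 29 visit" and section 9.5 stops at 29 days. Section 8.5 calls time to recovery the only time-to-event analysis. Shell 14.3.1 counts days from consent, but Table 5 counts from Day 1.

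The cost is SAP wording only, since protocol 7.1 already requires the reason for stopping to be documented. The downsides are slightly fewer composite events and reliance on the recorded reason.

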8 GENERAL STATISTICAL CONSIDERATIONS

8.1 Sample Size

This is a pilot study and it is not powered based on any specific endpoint. Sample size has been set to minimize the number of patients exposed, but still large enough to give reliable estimates on the efficacy and safety of ensifentrine in the target population.

8.2 General Principles

This is a double-blind, placebo controlled randomized pilot study which may inform on treatment effect for future studies.

All analyses are considered exploratory and hypothesis-generating. All tests will be two-sided at 5% significance level. Hypothesis tested for the primary endpoint will be if addition of ensifentrine to SoC for up to 29 days could increase the proportion of patients with recovery versus standard of care plus placebo. The status according to the 7-point ordinal scale of all patients regardless of treatment withdrawal will be followed up during the scheduled treatment period (Day 29) and at a follow-up Day 60, or as far as possible.

Secondary endpoints are tested independently and there will be no adjustment for multiple tests.

8.3 Analysis Populations

Summaries and analysis of safety data will be presented for the Safety Analysis Population.

Summaries and analysis of efficacy data will be presented for the intent-to-treat (ITT) population.

- Intent to treat (ITT): Will consist of all randomized patients. Efficacy will be evaluated as randomized.
- Per protocol population (PP): Will consist of all patients in ITT without any major protocol deviations (determined prior to database lock) deemed to have an effect on efficacy analyses.
- Safety set (SS): Will consist of all randomized and treated patients (at least one dose).
 Safety will be evaluated by actual treatment.

8.4 Subgroups

In an exploratory manner, we will perform subgroup analyses for outcomes (i.e. the primary and key secondary analyses) where possible (minimum size required) to evaluate the treatment effect across the potential subgroups listed below:

- COVID disease severity: Mild, Moderate, Severe or Critical disease (severe and critical may be combined).
- Randomization day (prior to 1st dose of study medication) clinical status assessed using the 7-point ordinal scale: 3, 4 or 5.
- Gender: Female, Male.
- Race: White; Black/African American; Asian; Other.

pg. 18 Confidential

- Baseline presence of comorbidities: None, One, Two or more.
- Age group: <40, 40-64, 65 and older (may use two age groups instead of three).
- Smoking history: Never, Current, Past.

8.5 Missing Data

All attempts will be made to collect all data per protocol.

 The patients withdrawn from treatment will be followed up regarding their status according to the 7-point ordinal scale at Day 29 as far as possible (exceptions for patients with withdrawn consent or lost to follow-up) and this data will be the primary source for handling missing data in the study.

Any data point that appears to be erroneous or inexplicable based on clinical judgment will be investigated as a possible outlier.

• If data points are identified as outliers, sensitivity analyses may be performed to examine the impact of including or excluding the outliers. Any substantive differences in these analyses will be reported.

For survival analyses, patients with death as outcome will be censored at Day 29 (Day 60), unless the required event was reached prior to death. Patients who are lost to follow-up or terminate the study prior to Day 29 (Day 60) for other reason than death and prior to observing/experiencing the event will be censored at the time of their last observed assessment.

The only time to event analyses is the time to recovery.

For secondary endpoint analyses, the following imputation rules will be used for patients who are lost to follow-up, terminate early from the study, or do not have further outcome data available after discharge for any reason than death:

- Patients with no data collected at the actual time point of interest for other reason than
 death, the last assessment of their status prior to this time point will be used as a
 representative for that time point. Especially, if the patient's clinical status scale is 1 or 2
 at the last observed assessment, then the patient will be considered to be recovered
 through Day 29.
- For endpoints assessing total time (oxygen or non-invasive ventilator care), the status for patients with no data collected for other reason than death, will be assumed unchanged from last assessment of the score up to last day in the definition of the endpoint (Day 29). Thus, no extra days will be added for patients without oxygen or patients without non-invasive ventilator care at last assessment.
- Patients that die in the study will be handled as worst case in all the analyses, that is they are considered to be on oxygen need, non-invasive and invasive mechanical ventilator need for all time points following the death.
- In analyses of oxygen need, patients in ventilator care (non-invasive or invasive mechanical) will be considered in oxygen need for the corresponding time period and patients with death as outcome will be considered in oxygen need for the remainder of the time period of evaluation.
- In analyses of non-invasive ventilator need, patients that require invasive mechanical ventilation will be considered also as having a non-invasive ventilator need. Patients with death as an outcome will be considered as having non-invasive ventilator need from

pg. 19 Confidential

time of death for the remainder of the time period of evaluation.

- In analyses of invasive mechanical ventilator need, patients with death as an outcome will be considered in invasive mechanical ventilator need for the remainder of the time period of evaluation
- The change from baseline in the 7-point ordinal scale will use the baseline score and the score at the endpoint using imputation for missing data as stated above, that is the last assessment of their status prior to this time point will be used.
- If the patient is discharged and no further hospitalization data are available, then the
 patient will be assumed to not have been readmitted. Thus, no additional imputed days
 on hospitalization will be added to the number of days recorded on available
 assessments for these patients.

8.6 Interim Analyses

No interim analyses will be performed.

8.7 Safety Analysis

Time to first combined event.

Any patients that are lost to follow-up or terminated early prior to experiencing any of the events will be censored at the day of their last observed assessment.

Patients who complete follow-up but do not experience any of the events will be censored at the day of their Day 29 visit.

pg. 20 Confidential

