Table 14.2.16: Summary of the Proportion of Patients Alive and with Oxygen Use at Days 7, 14 and 29 (or discharge, whichever was first), ITT

Proportion of Patie Oxygen Use (Scale		Enrolled (N=45)	Ensifentrine (N=30)	Placebo (N=15)
Day 7	Yes No		,	
Day 14	Yes No			
Day 29	Yes No			

Hospitalized patient supplemental oxygen = the 7-point ordinal scale score is equal to 4, 5, or 6. Not hospitalized patient supplemental oxygen = the 7-point ordinal scale score is equal to 2 (if required to have home oxygen).

pg. 60 Confidential

Table 14.2.17: Summary of the Proportion of Patients Alive and with non-invasive Ventilation or High Flow Oxygen Use at Days 7, 14 and 29 (or discharge, whichever was first), ITT

Proportion of Patier Ventilation or High (Scale=5)	nts with Non-invasive Flow Oxygen Use	Enrolled (N=45)	Ensifentrine (N=30)	Placebo (N=15)
Day 7	Yes No			
Day 14	Yes No			
Day 29	Yes No			

Non-invasive ventilation or high flow oxygen use = the 7-point ordinal scale score is equal to 5 or 6.

pg. 61 Confidential

Table 14.2.18: Proportion of Patients Alive and Receiving Invasive Mechanical Ventilation or Extracorporeal Membrane Oxygenation (ECMO, 7-point ordinal scale criteria #6) at Days 7, 14 and 29 (or discharge, whichever was first), ITT

Proportion of Patier (Scale=6)	nts with ECMO	Enrolled (N=45)	Ensifentrine (N=30)	Placebo (N=15)
Day 7	Yes No			
Day 14	Yes No			
Day 29	Yes No			

IMV = The 7-point ordinal scale score is equal to 6.

Table 14.3.1: Time to first composite AE

		Enrolled (N=45)	Ensifentrine (N=30)	Placebo (N=15)
Proportion of AE	Yes No			
Time to first composite AE ^a	Days from consent (SD) Median (min Max.)			

^a Consider those who experienced Adverse events

Table 14.3.2: Number/Proportion Treatment emergent adverse events

	Statistic	Total	Ensifentrine (N=30)	Placebo
TEAE Category			` ,	(N=15)
Any TEAE	N (%)			
Any TEAE leading to study medication discontinuation Any TEAE related to study medication				
Any serious TEAE				
Any serious TEAE leading to study medication discontinuation Any serious TEAE leading to death				
Any TEAE classified by maximum severity				
Mild				
Moderate				
Severe				
Any serious TEAE classified by maximum severity				
Moderate				
Severe				

Abbreviations: AE, adverse event; N, number of patients in treatment group; n, number of patients in analysis; TEAE, treatment-emergent adverse event; %, percentage of patients calculated relative to the total number of patients in the treatment group.

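### The SAP gives conflicting horizon, censoring and time-origin rules for time to first composite AE, and the time row of shell 14.3.1 does not report the endpoint as defined

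*SAP*

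**What the plan says.** Five places in the SAP bear on this endpoint.

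- **Section 7.2, Table 5 (Safety)** defines the time to the combined AE (death, SAE, severe AE, or early termination/withdrawal from study medication, ET/W) as "elapsed time (in days) from Day 1 to the earliest date of any of the events through hospitalization, Day 29 and Day 60".
- **Section 8.7** has two censoring rules. Patients who are "lost to follow-up or terminated early prior to experiencing any of the events will be censored at the day of their last observed assessment". For the rest, "Patients who complete follow-up but do not experience any of the events will be censored at the day of their Day 29 visit". There is no counterpart for Day 60.
- **Section 9.5** describes what is tested as "The time to the composite AE endpoint (death, SAE, severe AE or ET/W of treatment during first 29 days". It plans a log-rank comparison and a stratum-weighted difference in proportions between arms.
- **Section 8.5** states that recovery is the sole time-to-event analysis, which leaves no room for the analysis in 8.7 and 9.5.
- **Section 14, shell Table 14.3.1** has a Yes/No row by arm and a time row. The time row is labelled "Days from consent (SD", with a median and range, and carries the footnote "Consider those who experienced Adverse events". There is no cell for a log-rank p-value or a difference in proportions. The recovery shell, Table 14.2.5, does have a log-rank column.

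**The concern.** A time-to-event analysis needs one origin, one horizon and a censoring time that matches the horizon. Here Table 5 runs to Day 60, while the only rule for event-free completers stops at the Day 29 visit.

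Protocol 4.5 counts a patient as having completed the study only after both the Day 29 and Day 60 contacts. Protocol 8.6.1 collects adverse events to the end-of-study visit. A patient observed event-free to Day 60 would therefore lose about a month of observed time, while a patient with an event on Day 40 would keep it. Whether a patient is still at risk on Day 35 would then depend on what happens later, which is informative censoring.

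The shell raises a separate problem. A mean and median among patients with events is not an estimate of the defined endpoint, whichever horizon is meant.

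At stake is the one safety endpoint for which SAP 9.5 specifies a between-arm comparison. Two programmers working from this text could build different datasets.

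**Working it through.** **Plan's own figure.** There is none to reproduce. SAP 8.1 says the study is not powered on any endpoint, and no event count or rate is given for the composite. The arm sizes agree: 30 + 15 = 45, at 2:1.

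**Inputs from the documents.** Arms of 30 and 15 (SAP 6.1). Day 29 contact at 26 to 32 days and Day 60 contact at 55 to 65 days after first dose (Protocol 8.5). Screening 0 to 4 days before Day 1 (Protocol 1.3). Two-sided 5% tests (SAP 8.2).

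**Assumed inputs.** All event times below are assumptions.

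**Formulas.** Kaplan-Meier: S(t) = product of (1 − d/n) over event days. Log-rank, ensifentrine arm: E = sum of d·n1/n; V = sum of d·(n1/n)(1 − n1/n)(n − d)/(n − 1), with a zero contribution when n = 1; z = (O − E)/√V.

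**Step 1: both stop at Day 29.** Assume events on Days 3, 6, 9 and 15 on ensifentrine and Days 4 and 12 on placebo. Pooled S(29) = 39/45 = 0.867. Log-rank: O = 4, E = 4.0, V = 1.333, p = 1.000. Nothing is distorted, apart from a small effect of the 26 to 32 day window.

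**Step 2: events to Day 60, event-free patients censored at Day 29, one arm of 15.** Assume events on Days 3, 6, 10, 20 and 40, with 10 patients event-free.
- S(20) = 11/15 = 0.733.
- On Day 40 the risk set is 1, so S(40) = 0.733 × (1 − 1/1) = 0.000.
- With event-free patients followed to Day 60, S(60) = 10/15 = 0.667.

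**Step 3: the same mismatch, pooled.** Add two late events to Step 1. Under 8.7 the risk set at the first late event is 2 instead of 39.
- Censoring at Day 29: 0.867, then 0.867 × 1/2 = 0.433, then 0.000.
- Censoring at Day 60: 39/45 = 0.867, 38/45 = 0.844, 37/45 = 0.822.

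**Step 4: effect on the log-rank test.**

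| Late events (assumed) | p, event-free censored at Day 29 | p, event-free censored at Day 60 |
|---|---|---|
| One per arm (ensifentrine Day 40, placebo Day 50) | 0.691 | 0.808 |
| Both ensifentrine (Days 36, 44) | 1.000 | 0.613 |
| Both placebo (Days 36, 44) | 1.000 | 0.310 |

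In the first row, Day 29 censoring gives O = 5, E = 4.5, V = 1.583 and z = 0.397. Day 60 censoring gives O = 5, E = 5.325, V = 1.780 and z = −0.244, so the sign reverses. In the other two rows only one arm has anyone at risk after Day 29. Each late event then has observed equal to expected and zero variance, and the result is the Step 1 result.

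**Step 5: the shell's time row.** For the six early events, the events-only mean is 49/6 = 8.2 days and the median 7.5 days from Day 1. Counting from consent adds 0 to 4 days, so at most 12.2 and 11.5. Only 6 of 45 patients (13%) contribute. The Kaplan-Meier median is not reached, because 87% are event-free at Day 29.

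**The case against.** The strongest reply is that 9.5 and 8.7 agree with each other: the tested composite belongs to the first 29 days, and censoring is at Day 29. On that reading the log-rank test is sound, and the gap is only that Table 5 names a Day 60 window with no matching rule. This largely stands. It does not settle the matter, because the 29-day phrase in 9.5 may qualify only ET/W. Treatment ends by Day 29, so that narrower reading is natural. Table 5 would still need to change.

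A reader might infer three stronger things that the documents do not support.

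- **That a planned Day 60 curve will be wrong.** SAP Table 13 lists one Kaplan-Meier figure, for recovery. Protocol 10.5 makes AE plots optional and gives no horizon. The fall to 0.000 applies only if a Day 60 analysis is run under 8.7.
- **That the shell cannot show which arm has more events.** Its Yes/No row is given by arm and includes event-free patients. The footnote is attached only to the time row.
- **That the safety comparison rests on the log-rank test alone.** 9.5 also plans a difference in proportions, which does not use the censoring rule, although it does need a stated horizon.

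It is also fair that the composite is not among the Protocol's listed safety endpoints, that the shells are labelled as examples, and that SAP 12 allows additions. Permission to add output does not correct a wrong origin or a row limited to patients with events.

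**Conclusion.** The inconsistency is real, and its effect depends on which horizon is meant.

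- **Day 29 for both events and censoring:** the log-rank test is sound.
- **Day 60 events under the 8.7 rule:** the Day 60 estimate is invalid (0.000 against 0.667 in the one-arm illustration), and late events confined to one arm add nothing to the test. The exact zero assumes nobody is lost after Day 29. A patient lost later would be censored at a later assessment and would stay briefly at risk, hence essentially, not strictly, only patients with later events. The event times are assumed, but the mechanism does not depend on them.
- **On any reading:** the time row of shell 14.3.1 has an origin 0 to 4 days earlier than the definition and omits every censored patient, and the shell has no cell for either comparison planned in 9.5.

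Severity is low, because the analysis is exploratory, concerns safety, and sits in an unpowered pilot of 45 patients.

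**What to change.** 1. State the origin once as Day 1, in 7.2, 8.7, 9.5 and the shell.
2. For the 29-day analysis, stop both events and censoring at a fixed Day 29, not at a contact that may fall anywhere from 26 to 32 days. Reword 9.5 so that the 29-day limit clearly applies to the whole composite.
3. Decide on Day 60. If it is kept, define it as a separate analysis that censors event-free patients at the Day 60 contact or last assessment, and state the horizon for its difference in proportions. If not, remove Day 60 from the Table 5 definition.
4. In shell 14.3.1, replace the time row with Kaplan-Meier estimates from Day 1 on the whole Safety Set, with numbers at risk. Add the log-rank p-value and the difference in proportions. Keep the Yes/No row, labelled as the composite event.
5. Correct the 8.5 sentence so that it also names the composite AE analysis.

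The cost is SAP wording and one shell. No new data are needed, because adverse events are already assessed through the Day 60 contact.
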